## 9.1 Sample Size Calculation

The sample size calculation for the trial is based on the primary safety endpoints. The linearized rates for thromboembolism, all hemorrhage, all perivalvular leak, and endocarditis will be compared to the Objective Performance Criteria from Annex R, Table R.1 per ISO 5840 as proposed by the US FDA in the Heart Valve Guidance draft 2009. These OPC are presented in Table 11.

Adverse Event	OPC
Thromboembolism	2.5
All Hemorrhage	1.4
All Perivalvular Leak	1.2
Endocarditis	1.2

Table 11: Safety OPC

More specifically, a statistical test based on the Poisson distribution will be performed for each of these adverse event rates to evaluate whether it is less than 2 times the appropriate OPC. Thus, the null and alternative hypotheses for each adverse event are as follows:

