## $H_0: \lambda \geq 2 \cdot OPC$

## $H_A: \lambda < 2 \cdot OPC$

This document and the information contained herein is considered Proprietary and Confidential and may not be reproduced, used or disclosed without written permission from Edwards Lifesciences LLC.

where  $\lambda$  is the linearized rate for the given adverse event (thromboembolism, valve thrombosis, all hemorrhage, all perivalvular leak, and endocarditis) computed when the total subject years reaches 808 and *OPC* denotes the relevant OPC. The test statistic for each adverse event is of the form:

$$Z = (\lambda - 2 \cdot OPC) / \sqrt{\lambda} .$$

 $H_0$  is rejected in favor of  $H_A$  if Z is less than -1.645, the lower 5% percentile of the standard normal distribution. Grunkemeier, et al. have demonstrated that 800 subject life-years is adequate to test against the smallest OPC of 1.2% per subject year (excluding valve thrombosis, and stratification for major versus minor hemorrhage, and perivalvular leak) with Type I and Type II error controlled at the .05 and .20 levels, respectively.

The proposed subject enrollment is calculated to ensure that at least 101 subjects survive to 8 years post implant. These 8\*101 = 808 life years in addition to the life years from those subjects not surviving to 8 years will more than fulfill the 800 life-years required by Grunkemeier, et al..

Sample size calculation for primary effectiveness endpoint is based on a test of the hypothesis:

 $H_0: p \le 75\%$  $H_A: p > 75\%$ 

where *p* is the proportion of the subjects in NYHA Class I or Class II at 8 years post implant. The expected proportion of the alive subjects in NYHA class I or II at eight years is approximately 90%, based on 7 year follow up data for the Carpentier-Edwards PERIMOUNT 6900/6900P valve (this proportion is essentially constant across each annual visit). Based on this expected proportion, a sample size of 45 subjects provides 85% power to test the hypothesis that the true proportion is greater than 75% using an exact binomial test. Thus, the sample size of 101 subjects with NYHA data at 8 year post implant is more than adequate to provide sufficient power.

This document and the information contained herein is considered Proprietary and Confidential and may not be reproduced, used or disclosed without written permission from Edwards Lifesciences LLC.

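### The primary safety Z statistic leaves out exposure, so it has neither the stated 5% size nor, as defined, the stated 80% power

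*Combined protocol and SAP*

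**What the plan says.** Section 9.1 tests each of the four primary safety events "to evaluate whether it is less than 2 times the appropriate OPC". The OPCs in Table 11 are 2.5 (thromboembolism), 1.4 (all hemorrhage), 1.2 (all perivalvular leak) and 1.2 (endocarditis). The units appear where the text refers to "the smallest OPC of 1.2% per subject year".

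The symbol λ "is the linearized rate for the given adverse event", computed when total follow-up reaches 808 subject-years. The statistic is Z = (λ − 2·OPC)/√λ, and H0 is rejected "if Z is less than -1.645, the lower 5% percentile of the standard normal distribution". The section cites a published sample-size paper for 800 life-years being enough at the smallest OPC, "with Type I and Type II error controlled at the .05 and .20 levels".

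Sections 9.1 and 9.3.1 both call this a test based on the Poisson distribution, but neither gives another formula or a critical value. The reporting guideline reproduced in Appendix 1 defines a linearized rate as events divided by patient-years, often expressed per 100 patient-years.

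**The concern.** If X events occur in T subject-years, the estimated rate is X/T and its variance is λ/T. Dividing by √λ alone omits T. Three things follow: Z is not standard normal under H0, its value changes by a factor of 10 between percent and fractional units, and its scale does not sharpen as follow-up accumulates. The denominator √λ suits a count, but the plan defines λ as a rate.

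This is the decision rule for all four primary safety endpoints. Taken literally, it would usually fail a valve performing exactly at its OPC on any given endpoint. Read as a count, it would too often pass a valve whose true rate is twice the OPC. These are opposite errors, and which one occurs depends on a choice of units that the plan leaves open.

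**Working it through.** **Inputs.** OPC 2.5, 1.4 and 1.2 % per year (Table 11); margin 2·OPC; T = 808 subject-years; one-sided cut-off −1.645; stated errors 0.05 and 0.20 (all Section 9.1). The plan gives no alternative rate, so power is computed at true rate = OPC, which is an assumption.

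The count X is Poisson with mean 2·OPC·T at the H0 boundary and OPC·T under the alternative. At 808 years (8.08 hundred subject-years) the two means are:
- OPC 2.5: 40.40 and 20.20
- OPC 1.4: 22.62 and 11.31
- OPC 1.2: 19.39 and 9.70

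**1. The plan's own figure.** For OPC 1.2, an exact Poisson test first has size at most 0.05 and power at least 0.80 at 811 years (reject at ≤12 events; size 4.95%, power 81.6%). A normal test using exposure and the null variance, Z = (λ − 2·OPC)/√(2·OPC/T), at 808 years also rejects at ≤12 events, with size 5.1% and power 81.9%. So 800 years with errors 0.05 and 0.20 is approximately right for a Poisson test that uses exposure.

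**2. Printed Z, rates in % per year.** When the observed rate equals the OPC, Z = −OPC/√OPC = −√OPC, which is −1.58, −1.18 and −1.10 for OPC 2.5, 1.4 and 1.2. None is below −1.645. Solving λ − 2·OPC = −1.645·√λ gives

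√λ = [−1.645 + √(1.645² + 8·OPC)]/2.

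For OPC 1.2: √λ = (−1.645 + √12.306)/2 = 0.9315, so λ = 0.868 % per year. Then 0.868 × 8.08 = 7.01, so the rule rejects at ≤7 events. The cut-offs for 1.4 and 2.5 are 1.086 and 2.434 % per year (≤8 and ≤19 events). All three lie below the OPC itself.

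**3. Printed Z, rates as fractions per year.** For OPC 1.2 (0.012), an observed rate equal to the OPC gives Z = −√0.012 = −0.11. The cut-off is 0.17 events in 808 years for OPC 1.2, 0.23 for 1.4 and 0.72 for 2.5. No result with one or more events can reject, and Z is undefined at zero events.

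**4. λ and 2·OPC read as event counts over 808 years.** This equals restoring T as √(λ/T). It rejects at ≤31, ≤16 and ≤13 events.

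**5. Results at 808 subject-years.** Size = P(X ≤ c | 2·OPC·T); power = P(X ≤ c | OPC·T).

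| Rule | OPC 2.5: c, size, power | OPC 1.4: c, size, power | OPC 1.2: c, size, power |
|---|---|---|---|
| Printed, % per year | 19, 0.01%, 45% | 8, 0.04%, 21% | 7, 0.12%, 25% |
| Count reading | 31, 7.6%, 99.1% | 16, 9.4%, 93.2% | 13, 8.4%, 88.6% |
| T restored, null variance | 29, 3.8%, 97.6% | 14, 3.7%, 83.0% | 12, 5.1%, 81.9% |
| Exact Poisson | 29, 3.8%, 97.6% | 14, 3.7%, 83.0% | 11, 2.9%, 73.1% |

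**6. More follow-up.** Under the printed percent rule at OPC 1.2, power falls to 15% at 1,200 years and 9% at 1,600, because the cut-off rate stays below the OPC while the estimate becomes more precise.

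**7. An illustration from the documents.** Model 6900P had 13 late bleeding events in 856.24 late patient-years, 1.518 % per year (Appendix 9, Table 4). Event definitions may differ from this study's. Against 2 × 1.4:
- Percent units: (1.518 − 2.8)/√1.518 = −1.04 (fail)
- Fractional units: −0.10 (fail)
- Counts: 0.028 × 856.24 = 23.97, and (13 − 23.97)/√13 = −3.04 (pass)
- Exact Poisson: P(X ≤ 13 | 23.97) = 0.011 (pass)

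**The case against.** The strongest reply is that the formula is shorthand. The text twice names a Poisson-based test and says only that the statistic is "of the form" shown. √λ is the standard deviation of a Poisson count, so an analyst would naturally work with counts over 808 years. Power is then 88.6% to 99.1%, and only the size is wrong. This stands as to power, but the count reading contradicts the stated definition of λ and still has a size of 7.6% to 9.4%.

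Several narrower points also stand:
- The 0.05 and 0.20 figures are credited to a cited paper and cover the smallest OPC only, so the low powers at 1.4 and 2.5 contradict no explicit claim. They are still the powers of the printed rule.
- In percent units, type I error is controlled and the test is only far too conservative.
- A valve at its OPC would usually fail each test taken singly, but not all four together. Assuming independence, that chance is 0.751 × 0.751 × 0.795 × 0.547 ≈ 25%.
- The exact test's 73% power at OPC 1.2 reflects discreteness at exactly 808 years. Section 9.1 expects further life-years from subjects who do not reach 8 years.
- The null-variance form is a smaller edit and nearly keeps both stated error rates at 808 years.

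None of these makes the printed statistic correct.

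**Conclusion.** The concern holds, and the rule must be corrected before it is used. No reading of the printed statistic gives 5% size at 808 subject-years: it is 0.01% to 0.12% in percent units, effectively zero in fractional units, and 7.6% to 9.4% as counts. Under the plan's own definition of λ as a rate, power at the smallest OPC is 25% or practically nil, against the 80% on which the design rests.

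These figures assume Poisson counts, analysis at exactly 808 subject-years and, for power, a true rate equal to the OPC. The fault is confined to the statistic; the exposure requirement is broadly reproducible.

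**What to change.** In Sections 9.1 and 9.3.1, replace the Z rule with an exact one-sided Poisson test. With x events in T subject-years, reject H0 if P(X ≤ x | 2·OPC·T) ≤ 0.05. Equivalently, reject if the one-sided 95% upper Poisson limit for x/T is below 2·OPC. State the units of λ and the OPC, define T, and tabulate the critical counts: at 808 years, ≤29 for thromboembolism, ≤14 for hemorrhage, and ≤11 for perivalvular leak and for endocarditis. State the assumed true rate and restate power at the T actually used.

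The cost is SAP wording and a small table, with no new data. At exactly 808 years the exact test has 73% power at OPC 1.2. It first reaches 80% at 811 years and stays at or above 80% from 912 years (checked to 1,499). If the sponsor prefers a normal form, √(2·OPC/T) as denominator gives 5.1% size and 81.9% power there at 808 years, so the small excess over 5% should be stated. Inserting T while keeping the observed rate in the variance is not enough, because size stays at 7.6% to 9.4%.

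### At 800 or 808 subject-years no event-count cut-off delivers the stated 0.05 / 0.20 error rates for the 1.2% OPC; the miss is small, and testing on all accrued exposure removes it

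*Combined protocol and SAP*

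**What the plan says.** Section 9.1 bases the sample size on the four primary safety rates. For each event type, "a statistical test based on the Poisson distribution will be performed for each of these adverse event rates", with the aim "to evaluate whether it is less than 2 times the appropriate OPC". Table 11 sets the OPCs, in percent per subject-year, at 2.5 for thromboembolism, 1.4 for all hemorrhage, and 1.2 for both all perivalvular leak and endocarditis.

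The rate is "computed when the total subject years reaches 808". The null is rejected "if Z is less than -1.645, the lower 5% percentile of the standard normal distribution", where Z is the observed rate minus twice the OPC, divided by the square root of the observed rate.

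The exposure is justified by citation: "800 subject life-years is adequate to test against the smallest OPC of 1.2% per subject year", "with Type I and Type II error controlled at the .05 and .20 levels, respectively". The same section adds that 101 eight-year survivors supply 808 years and that subjects who die earlier will add more. Section 9.2 includes all data up to explant or death. The plan states no true rate for the power claim, no joint power, and no rule on whether all four tests must reject.

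**The concern.** The adequacy of the exposure rests on a reference, with no calculation shown. It is stated as a pair of error limits for the smallest OPC, and that OPC governs two of the four primary safety endpoints. With about 10 events expected if the valve performs at the OPC and about 19 at the null boundary, the Poisson distribution moves in large steps. A nominal 0.05 / 0.20 pair may therefore not be attainable at a given exposure.

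At stake is whether the stated error rates describe the test that will be run. The plan also fixes the computation at 808 years while expecting and including more exposure, so a reader cannot tell which exposure the error rates refer to.

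**Working it through.** **Inputs.** From section 9.1 and Table 11: one-sided level 0.05; stated Type II error 0.20; null rate 2 × OPC, so 0.024 per year for the 1.2% endpoints; exposure T = 800 (cited) or 808 (used). Assumed: true rate equal to the OPC, 0.012 per year.

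**Formulas.** For a rule that rejects at c or fewer events, size = P(X ≤ c | mean 0.024·T) and power = P(X ≤ c | mean 0.012·T), with X Poisson.

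**Reproducing the plan's figure.** The smallest T with size ≤ 0.05 and power ≥ 0.80 has c = 12 and T = 810.1, so 811 whole years. That is 1.3% above 800 and 0.3% above 808, so the cited figure is reproduced closely but not exactly. The usual normal formula, ((1.645·√0.024 + 0.842·√0.012) / 0.012)², gives 836.

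**At the plan's own exposures** (null means 19.2 and 19.392; means at the OPC 9.6 and 9.696):

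| Reject at | Size, 800 | Power, 800 | Size, 808 | Power, 808 |
|---|---|---|---|---|
| ≤ 11 | 0.0315 | 74.1% | 0.0288 | 73.1% |
| ≤ 12 | 0.0556 | 82.8% | 0.0511 | 81.9% |
| ≤ 13 | 0.0911 | 89.2% | 0.0845 | 88.6% |

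No row meets both limits at either exposure.

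**The plan's Z.** As printed it has no exposure term: on the percent scale an observed 1.2 gives (1.2 − 2.4)/√1.2 = −1.10, which does not reject. Put on counts at 808 years, 13 events give (13 − 19.392)/√13 = −1.77, which rejects, and 14 give (14 − 19.392)/√14 = −1.44, which does not. The cut-off is therefore 13, the bottom row. With the null variance instead, 12 events at 808 give (12 − 19.392)/√19.392 = −1.68, so that version rejects at ≤ 12.

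**Other endpoints at 808, exact test.** Hemorrhage: null mean 0.028 × 808 = 22.6, cut-off 14, size 0.037, power 83.0%. Thromboembolism: null mean 0.05 × 808 = 40.4, cut-off 29, size 0.038, power 97.6%.

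**How exact power for the 1.2% OPC changes with exposure.** At 811 years the cut-off becomes 12 (size 0.0495, power 81.6%). Power falls below 80% again at 826–861 and at 900–911 years, and stays above from 912.

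**Expected exposure.** With 250 subjects, 56% eight-year survival and 15% loss (section 9.1), and assuming constant hazards and follow-up cut at 8 years, h = −ln(0.56)/8 − ln(0.85)/8 = 0.0928 and exposure = 250·(1 − e^(−8h))/h ≈ 1,412 years. There the cut-off is 24, size 0.048 and power 96%. If the lost 15% contribute nothing, exposure is about 1,290; with no loss, about 1,520.

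**Joint power (supplementary).** At 808, if the endpoints are independent and every true rate equals its OPC, the chance that all four reject is 0.976 × 0.830 × 0.731² = 0.43. Without independence it lies between 0.976 + 0.830 + 0.731 + 0.731 − 3 = 0.27 and 0.73.

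**The case against.** The strongest reply is that the exposure target is essentially right. The exact requirement is 811 years, three more than planned, and at 808 the 12-event rule exceeds 0.05 by only 0.0011 while giving 82% power. This stands. A reader might infer that the safety study is materially under-sized; the documents do not support that, because section 9.1 expects more than 808 years and section 9.2 keeps all data to explant or death.

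A reader might also infer that the planned test has 73% power. It does not: 73% belongs to a strict exact test. The plan's Z on counts has 89% power, and its weakness is a size of 8.4–9.1%. The null-variance version has 82% power at size 5.1%. What remains is that none of these versions delivers both stated error rates.

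The 43% joint figure invites the reading that the plan misstates its overall power. It does not: the 0.20 is claimed for a single comparison, and the documents give neither a must-pass-all rule nor a joint power. The figure also depends on the assumed true rates. At the late rates reported for the predecessor valves (Appendix 4, Model 7300TFX instructions, Tables 1 and 2), exact joint power at 808 under independence is 99.6% for model 6900, whose hemorrhage figure covers only anticoagulant-related bleeding. For model 6900P it is 76%, limited by bleeding at 1.5% per year.

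Finally, the cited paper is not available here and may have used another true rate or approximation. That is a reason to state the inputs in the plan.

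**Conclusion.** The concern holds in a limited form. Taking the true rate as the OPC, the 0.05 / 0.20 pair claimed for the 1.2% OPC is not attainable at 800 or 808 subject-years. Holding the size at or below 0.05 costs 6 to 7 points of power for perivalvular leak and endocarditis; keeping the power means a size of 5.1–5.6% (12 events), or 8.4–9.1% with the plan's Z on counts. Hemorrhage and thromboembolism exceed 80% at 808.

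This is a discreteness effect that three more years would cure at that point, so it does not show a failed design. It merits correction because the plan prints error rates its test does not have, ties the test to 808 years while expecting more exposure, and can obtain ample power from data it already intends to collect. The gain at about 1,412 years rests on constant hazards and the plan's own survival and loss figures.

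**What to change.** In section 9.1:

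- Replace the Z rule with an exact one-sided 0.05 Poisson test on event counts, and state the assumed true rate.
- Replace the 800-year adequacy sentence with exact size and power. At 808 years and true rates at the OPC, power is 73% for perivalvular leak and endocarditis, 83% for hemorrhage and 98% for thromboembolism.
- Replace the 808-year trigger with all exposure accrued at the final analysis, with a minimum of 811 years. A minimum of 912 is safer because exact power for the 1.2% OPC is then at least 80% at every larger exposure.
- State power at the expected exposure: about 96% per 1.2% endpoint at roughly 1,400 years, with the assumptions listed.
- Say whether the safety objective requires all four tests to reject. If it does, report joint power as a supplement, with its independence assumption and the range without it.

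The cost is revised wording and one recalculation. No subjects or follow-up are added. The one drawback is that the power printed for 808 years looks less favourable than the current text.

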# 1.0 STUDY SUMMARY

Protocol No:	2006-05	
Study Title	Post Approval Study 2006-05 Carpentier-Edwards ® PERIMOUNT ® Magna Mitral Pericardial Bioprostheses Models 7000/7000TFX and Carpentier- Edwards ® PERIMOUNT ® Magna Mitral Ease™ Pericardial Bioprostheses Models 7200TFX and 7300/7300TFX	
Study Purpose:	Jy Purpose: To evaluate the long term safety and effectiveness of the Carpentier-Edward PERIMOUNT ® Magna Mitral Bioprostheses Models 7000/7000TFX and the Carpentier-Edwards ® PERIMOUNT ® Magna Mitral Ease ™ Pericardial Bioprostheses Models 7200TFX and 7300/7300TFX in patients undergoing mitral valve replacement with or without concomitant procedures requiring cardiopulmonary bypass.	
Study Device:	Carpentier-Edwards ® PERIMOUNT ® Magna Mitral Pericardial Bioprostheses, Models 7000/7000TFX and Carpentier-Edwards ® PERIMOUNT ® Magna Mitral Ease™ Pericardial Bioprostheses Models 7200TFX and 7300/7300TFX	
Study Design:	This is a prospective, single-arm, multi-center study to be conducted in the US and outside the US (OUS). This study will enroll a minimum of 250 subjects implanted with the study valve in order to achieve 101 mitral valve replacement subjects who complete follow-up for a minimum of 8 years.	
Study Population:	Male and female patients, 18 years or older, requiring replacement for a diseased, damaged, or malfunctioning native or prosthetic mitral valve.	
Entry Criteria:	Patients will preoperatively sign the subject informed consent form, and meet all inclusion criteria and none of the exclusion criteria to participate in this clinical study.	
Duration of Participation:	After the valve implantation, subjects will be followed and assessed at discharge, 6-months, one year, and annually thereafter for a minimum of 8 years.	

	Primary Safety
Clinical Endpoints:	Linearized rates of:
	Thromboembolism
	All hemorrhage
	All perivalvular leak
	Endocarditis
	Secondary Safety
	Early and late linearized and actuarial rates of:
	Thromboembolism
	Valve thrombosis
	All hemorrhage
	Major hemorrhage
	All perivalvular leak
	Major perivalvular leak
	Endocarditis
	Hemolysis
	Structural valve deterioration
	Non-structural valve dysfunction
	Reoperation
	Explant
	Death
	Valve-related death
	Blood Studies to assess hemolysis and adverse events.
	white blood count
	red blood count
	hematocrit

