#### 6.8 Valve Explants

Every effort should be made to return the explanted valve(s), at autopsy or explantation to Edwards. The explanted valve should be placed in a container with a suitable histological fixative such as 10% formalin or 2% glutaraldehyde immediately after excision and returned to Edwards. Refrigeration is not necessary under these circumstances. Contact Edwards Clinical Research for additional instructions.

Any pertinent information, e.g. operative notes, autopsy report etc should be sent to Edwards. All supporting data should be de-identified at the site to protect the privacy of the study subject.

This document and the information contained herein is considered Proprietary and Confidential and may not be reproduced, used or disclosed without written permission from Edwards Lifesciences LLC.

After the study valve is explanted, the subject will be followed for either an additional 30 days to monitor for any new adverse events or until all study device related serious adverse events are resolved. After that point the subject will be discontinued from the study. No further evaluations and/or case report forms are needed after study exit. Data from these subjects will be included in analysis

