The calculated number of subjects (n) that must be enrolled in order to have 101 subjects survive to 8 years post implant with 99% probability is based on the binomial distribution. Specifically, n is such that

$$1 - \sum_{x=1}^{101} {n \choose x} p^x (1-p)^{n-x} > 98.7\%$$

where *p* is the probability that a subject will survive for 8 years post implant. This calculation can be performed using standard statistical software. Based on the reported 8-year survival of 56% from Thourani, et al. , a sample size of 212 subjects fulfills the requirements of the equation above. Based on the data collected in a previous post approval study conducted by Edwards (Study 98-1), a lost to follow-up rate of 7.8% was observed among subjects who reached 5 or more years of follow-up post implant. The sample size is further inflated to 250 to account for up to a 15% rate of lost to follow up.

The STS Executive Summary indicated that 15% of patients undergoing mitral valve surgery in 2007 in the United States underwent simultaneous mitral and aortic valve replacement (1205/7883). In order to reflect actual market use of the Carpentier-Edwards PERIMOUNT Magna Mitral valve, of the 250 subjects enrolled in the study, approximately 38 are anticipated to be those patients eligible for simultaneous aortic and mitral valve replacement.

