#### Table 1: Observed Adverse Event Rates for MVR and DVR (Model 6900)

An patients analyzed. N = 305 Cumulative follow-up. 1100 patient-years							
	Early I	Events	Late	Events 	Freedo	m from Event (%) [9	5% CI] 
Complication	n 	%	n	%/ptyr.	1 year (n = 287)	5 years (n = 141)	8 years (n = 18)
Mortality (all)	34	9.4	50	4.7	85.5 [81.8, 89.2]	75.4 [70.3, 80.6]	65.4 [57.6, 73.2]
Valve-related events							
Mortality (valve-related)	0	0	16	1.5	97.7 [96.0, 99.4]	95.3 [92.8, 97.8]	91.9 [87.5, 96.4]
Explants	0	0	8	0.7	98.7 [98.0, 99.3]	96.7 [95.3, 98.0]	95.6 [93.9, 97.3]
Reoperations	2	0.6	12	1.1	97.1 [96.2, 98.1]	95.1 [93.6, 96.6]	93.0 [90.9, 95.1]
Anticoagulant-related hemorrhage	2	0.6	9	0.8	97.1 [95.2, 99.0]	97.1 [95.2, 99.0]	94.1 [88.2, 100]
Endocarditis	1	0.3	3	0.3	99.0 [97.9, 100]	98.7 [97.4, 98.9]	98.7 [97.4, 98.9]
Hemolysis	0	0.0	1	0.1	99.7 [99.0, 100]	99.7 [99.0, 100]	99.7 [99.0, 100]
Nonstructural dysfunction	0	0.0	3	0.3	100 [100, 100]	99.3 [98.0, 100]	98.3 [95.9, 100]
Perivalvular leak (all)	1	0.3	5	0.5	98.4 [97.0, 99.8]	98.4 [97.0, 99.8]	97.3 [94.9, 99.8]
Structural valve deterioration	0	0.0	5	0.5	100.0 [100, 100]	97.6 [95.2, 100]	92.8 [85.3, 100]
Thromboembolism	5	1.4	8	0.7	97.5 [95.8, 99.2]	96.1 [93.8, 98.5]	96.1 [93.8, 98.5]
Thrombosis	0	0.0	0	0.0	100.0 [100, 100]	100.0 [100, 100]	100.0 [100, 100]

1. Late event rates were calculated as linearized rates (%/pt-yr) based on 1072.5 late patient-years (> 30 days postoperatively).

2. Freedom from event rates were calculated using the Kaplan-Meier method. Greenwood's formula was used for calculation of the standard errors of these estimates

n = number of events.

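### Section 9.1 counts eight-year survival as completed follow-up: with explants included, the 99% assurance of 101 subjects is about 95% at the plan's own values, and missing NYHA assessments are not allowed for

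*Combined protocol and SAP*

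**What the plan says.** The Study Summary (Section 1.0) gives the purpose of enrolling at least 250 subjects: "in order to achieve 101 mitral valve replacement subjects who complete follow-up for a minimum of 8 years". Section 9.1 turns this into a survival calculation. It seeks the number to enrol "in order to have 101 subjects survive to 8 years post implant with 99% probability", and defines p so that it "is the probability that a subject will survive for 8 years post implant". With the "reported 8-year survival of 56"% from a published cohort, it finds that "a sample size of 212 subjects fulfills the requirements of the equation above". It then raises 212 to 250 for loss of up to 15%, citing an observed loss of 7.8% in an earlier post-approval study among subjects who had reached at least 5 years.

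Section 6.8 follows an explanted subject for a further 30 days or until device-related serious events resolve, and then: "After that point the subject will be discontinued from the study". In the justification under Section 4.2, the sponsor itself groups valve removal with death and withdrawal as lost follow-up.

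For effectiveness, Section 9.1 says that "the sample size of 101 subjects with NYHA data at 8 year post implant is more than adequate to provide sufficient power". Section 9.2 restricts the primary effectiveness analysis to survivors with an eight-year NYHA assessment. Section 9.7 plans an available-case analysis, last observation carried forward (LOCF), and resampling from subjects with the same preoperative and last-available class.

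**The concern.** Three different counts share the number 101: subjects alive at 8 years, subjects completing eight-year follow-up, and subjects with an eight-year NYHA class. The calculation covers the first and, through the 15%, part of the second. Explant ends participation but is in neither the 56% nor the 15%. A missed NYHA assessment in a subject still in follow-up is not covered at all.

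Two things are at stake: whether the stated assurance is correct for the count that the study needs, and how firmly the 75% NYHA test can be read if many living subjects have no eight-year class.

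**Working it through.** **Inputs**
- Survival 56%, loss allowance 15%, cited loss 7.8%: Section 9.1.
- Model 6900, eight-year freedom from explant: "95.6 [93.9, 97.3" (per cent, with 95% limits), with 18 subjects at risk at 8 years. Eight-year survival in the same table is 65.4%. Source: Appendix 4, instructions for use for model 7300TFX, Table 1.
- Model 6900P, late explant rate 0.9% per patient-year: same instructions, Table 2. If constant (an assumption), exp(−0.009 × 8) = 0.931, about 93% free of explant at 8 years.
- NYHA not available at 5 years: 63/129 = 48.8% (6900) and 27/96 = 28.1% (6900P). Source: Appendix 9, Tables 7 and 8.

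**The plan's own figure reproduces.** As printed, the formula sums to x = 101, so it requires at least 102 survivors. With X ~ Binomial(212, 0.56), P(X ≥ 102) = 99.1% and P(X ≥ 101) = 99.4%. Then 212/0.85 = 249.4, rounded up to 250. Directly, p = 0.56 × 0.85 = 0.476, and Binomial(250, 0.476) gives P(X ≥ 101) = 99.1%, with 119 expected.

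**Adding explants.** Take p = survival × freedom from explant × (1 − loss), assuming independence, with n = 250 and 56% survival.

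| Freedom from explant | Loss | p | Expected | P(≥ 101) |
|---|---|---|---|---|
| not considered | 15% | 0.4760 | 119.0 | 99.1% |
| 95.6% | 15% | 0.4551 | 113.8 | 95.4% |
| 93% | 15% | 0.4427 | 110.7 | 90.3% |
| 95.6% | 7.8% | 0.4936 | 123.4 | 99.8% |

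With 95.6% freedom from explant, the assurance stays at 99% up to a loss of about 11.2%. Restoring 99% at 15% loss would take 262 subjects.

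**Subjects with an eight-year NYHA class.** Here the missing fraction replaces the 15%, and explant freedom is 95.6%. The source tables give no reasons for unavailable assessments, so carrying 28.1% and 48.8% forward to year 8 of this study is an assumption.

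| Survival | Missing | p | Expected assessed | P(≥ 101) |
|---|---|---|---|---|
| 56% | 15% | 0.4551 | 113.8 | 95.4% |
| 56% | 28.1% | 0.3849 | 96.2 | 28.8% |
| 56% | 48.8% | 0.2741 | 68.5 | about 0% |
| 65.4% | 15% | 0.5314 | 132.9 | > 99.9% |
| 65.4% | 28.1% | 0.4495 | 112.4 | 93.5% |
| 65.4% | 48.8% | 0.3201 | 80.0 | 0.3% |

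**Power.** With 45 assessed, the exact test passes at 39 or more in class I/II and has 84.1% power at a true 90% (the plan says 85%). In the least favourable row, with p = 0.2741, P(at least 45 assessed) = 99.98%. Follow-up time is also safe: at p = 0.4551 the expected completers alone give 113.8 × 8 = 910 subject-years, above the 800 required.

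**Reading the 75% test.** Suppose 90% of those assessed are in class I/II. The proportion of missing subjects who must also be in class I/II for the overall point estimate to reach 75% is:
- 28.1% missing: (0.75 − 0.90 × 0.719)/0.281 = 37%.
- 48.8% missing: (0.75 − 0.90 × 0.512)/0.488 = 59%.
- 15% missing: none, since 0.90 × 0.85 = 76.5%. A point estimate at that level would still not pass the exact test.

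**The case against.** The strongest reply is that nothing is miscalculated. The 99% is attached to survival, p is defined as survival, and 212 and 250 both reproduce. The 15% is a ceiling above an observed 7.8%. Loss of 7.8% with 4.4% explants makes combined attrition 1 − 0.922 × 0.956 = 11.9%, which fits inside 15%. The table that supplies the explant figure also gives 65.4% survival, and with both rows and 15% loss the chance of 101 completers exceeds 99.9%. Enrolment is a minimum, and Section 4.2 ties the final report to reaching 101.

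Much of this stands. The shortfall exists at the planning values, not under every documented input, and the eight-year explant estimate rests on 18 subjects at risk. But 7.8% applies only to subjects who had already reached 5 years, so it may understate cumulative loss, and the plan chose 56% and 15% as its own basis. Nor does reading the 99% as survival rescue it as an assurance of completed follow-up, which is the stated goal.

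A reader might go further and infer that the 28% to 49% unavailable NYHA shows the 15% loss allowance to be wrong. The documents do not support that. An unavailable assessment at a visit is not a lost subject, the only loss rate cited is 7.8%, and the 6900 data pool studies implanted between 1984 and 1997. Those figures bear only on the description of the 101 as having NYHA data.

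It is also fair that Section 9.7 is not bare. LOCF keeps a subject's own last class, so a class III or IV subject remains a failure, and the resampling matches on NYHA history. Among those assessed at 5 years, 65/66 and 63/69 were in class I/II, so treating every missing subject as a failure is an extreme bound. What none of the three analyses tests is whether unobserved subjects fare worse than observed subjects with the same history.

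**Conclusion.** The concern holds in a limited form. Section 9.1 equates survival with completed follow-up and leaves out explants. At 56% survival and 15% loss, the chance of at least 101 completers among 250 is about 95%, or about 90% if the 6900P late explant rate stays constant. The stated 99% needs loss of about 11% or less. These figures assume that death, explant and loss are independent.

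The second part is separate: the claim of 101 subjects with NYHA data has no allowance for missing assessments. If predecessor missingness recurred, the claim would fall short of 99% at either survival figure, though by very different amounts.

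It would be wrong to conclude that the study is underpowered or that the 99% fails under any reasonable input. Power for the NYHA test and the subject-years for safety are not threatened. The matter is a stated assurance that should be corrected and a sensitivity analysis that should be added.

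**What to change.** In Section 9.1:
- Define p as alive, unexplanted and in follow-up at 8 years, and state the explant assumption and its source.
- Restate the assurance for 250 subjects as about 95% at 15% loss and 99.8% at 7.8%.
- Give the expected number with an eight-year NYHA class under 15%, 28% and 49% missing: about 114, 96 and 69 at 56% survival, and 133, 112 and 80 at 65.4%. Reword the sentence that takes 101 with NYHA data as given.

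In Section 9.7, add a tipping-point analysis of the 75% test among living subjects with the valve in place. It should show how low the class I/II proportion among missing subjects can go before the conclusion changes, with missing-equals-failure as the extreme bound.

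The cost is a less favourable stated figure and one extra table. No added enrolment is needed.
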